7.3 PRIMARY ENDPOINT

For the primary endpoint, the percentage of patients with therapeutic success will be presented together with the 95% confidence interval. The number and percentage of patients with and without therapeutic success will be calculated for the whole FAS set.

The PF-10, represented by the physical functioning subscale of the Short Form 36 (SF-36), ranges from 0 to 100. A higher score indicates a better physical functioning. The score is calculated as followed:

Answer to questions 01- 10	Score
Yes, limited a lot	1
Yes, limited a little	2
No, not limited at all	3

Transformed scale = [(Sum of final item values – 10) * 100] / 20

7.4 SECONDARY ENDPOINT(S)

All analysis will be descriptive and will be performed on FAS. For general condition of patients and patient's satisfaction with Spiolto® Respimat®, the number and percentage of patients within each category will be displayed. For absolute changes in PF-10 score, summary statistics, a frequency table and a normality test (Shapiro-Wilk test) will be provided.

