9.7.3 Planned analyses

All patients who have received at least one dose of Spiolto[®] Respimat[®] will be included in the analysis; this is the treated set. All analyses will be performed on the treated set (as-treated analysis). If patients have missing values for an outcome, those patients will be excluded for that outcome's analysis.

The assessment will be carried out using SAS[®] software. The statistical characteristics presented in the end-of-text tables will be N / mean / SD / min / median / max for continuous variables. Tabulations of relative and absolute frequencies will be presented for categorical variables. Incidence rates and 95% CI will be given when appropriate.

The analyses will relate to the following data as recorded in the eCRF:

- Patient demographics (age, gender, height, and weight)
- Comorbidities
- COPD related and other concomitant medication
- History of smoking
- Reported exacerbations
- Breathlessness based on mMRC score
- Physical Functioning based on PF-10 scores (therapeutic success at visit 2); primary outcome
- Changes from visit 1 to visit 2 in the PF-10 score; secondary outcome
- Patient satisfaction with Spiolto[®] Respimat[®] at visit 2 only; secondary outcome

- General condition of the patient: evaluated by the physician (Physician's Global Evaluation (PGE)); secondary outcome
- Adverse Drug Reactions (ADR & SADR), fatal AEs, pregnancies
- GOLD spirometric classification (1,2, 3, 4)
- GOLD patient groups (A, B, C, D)
- Details of treatment with inhaled respiratory agents before the study
- Details of treatment with respiratory agents during the study
- Reasons for ending treatment during the observation period
- Details of treatment continuation / discontinuation

Main analysis

For the primary outcome, the proportion of patients with therapeutic success will be presented together with the 95% confidence interval.

Further analyses

The patient's general condition (PGE) at visit 1 and visit 2, mMRC at visit 1 and patient satisfaction at visit 2 are categorical variables so they will be analyzed as tabulations of frequencies. Change from visit 1 to visit 2 in the PF-10 score is a continuous outcome, so it will be analyzed with N / mean / SD / min / median / max.

The safety data will be reported according to local requirements.

As similar studies will also be performed in other European countries, data pooling might be considered at the end.

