9.10.1.3 Records

Case Report Forms (CRFs) for individual patients will be provided by the sponsor via remote data capture. All of the clinical data and site/investigator characteristics will be captured via a web-based Electronic Data Capturing system. The site staff will enter and edit the data via a secure network, with secure access features (username, password and secure identification – an electronic password system). A complete electronic audit trail will be maintained.

Patients must not be identified on the eCRF by name. Appropriately coded identification (i.e. Patient numbers) must be used.

All patient questionnaires will be paper-based and will be left at the site upon completion by the patient.

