4. CHANGES IN THE PLANNED ANALYSIS OF THE STUDY

- New analyses set, which is not mentioned in the protocol (Details are displayed in section 6.3):
 - Full analysis set (FAS)

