6.3 PATIENT SETS ANALYSED

Full analysis set (FAS): All screened patients with informed consent, date of registration, at least one documented administration of Spiolto® Respimat® and available PF-10 score at visit 1 and visit 2.

Treated set (TS): All screened patients with informed consent, date of registration and at least one documented administration of Spiolto® Respimat®.

Table 6.3.1 Patient sets analysed

Class of endpoint	Patient set	
	TS	FAS
Primary and secondary endpoints		X
Safety endpoints	X	
Demographic/baseline	X	

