6.7 BASELINE, TIME WINDOWS AND CALCULATED VISITS

Baseline visit (Visit 1) will include historical and demographic data as well as registration and initial examination. Treatment with Spiolto® Respimat® will be documented at visit 2 after approximately 6 weeks of treatment.

Proprietary confidential information © 2019 Boehringer Ingelheim International GmbH or one or more of its affiliated companies

The mMRC breathlessness scale is completed by the patient at visit 1 and PF-10 questionnaire at visit 1 and 2 as well as satisfaction survey at visit 2. In addition, the PGE is completed by the physician at visit 1 and visit 2.

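### The SAP reports physician's global evaluation and patient satisfaction only in patients with a PF-10 score at both visits, against the protocol's outcome-by-outcome rule and without a stated reason

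*SAP*

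**What the plan says.** Protocol section 9.7.3 sets one rule for every outcome: "All analyses will be performed on the treated set (as-treated analysis"). A patient with a missing value is left out of that outcome's analysis only. PGE and satisfaction are listed in that section as secondary outcomes.

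The SAP changes this. Section 4 announces a "New analyses set, which is not mentioned in the protocol", the FAS, and refers to section 6.3 for details. There the FAS carries the treated-set conditions (consent, registration date, and "at least one documented administration of Spiolto® Respimat") plus one more: "and available PF-10 score at visit 1 and visit 2". Table 6.3.1 assigns all primary and secondary endpoints to the FAS, and section 7.4 repeats this for the secondary endpoints: "All analysis will be descriptive and will be performed on FAS". Neither section 4 nor section 6.3 gives a reason.

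Three other statements matter:

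- SAP section 6.7 on who rates PGE: "In addition, the PGE is completed by the physician at visit 1 and visit 2".
- SAP section 6.7 on treatment records: "Treatment with Spiolto® Respimat® will be documented at visit 2 after approximately 6 weeks of treatment".
- Protocol section 9.10.1.3 on the patient forms: "All patient questionnaires will be paper-based and will be left at the site upon completion by the patient".

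SAP section 6.6 sets the PF-10 score to missing when half or more of its items are blank, that is, 5 or more of 10.

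**The concern.** PGE and satisfaction are the two secondary objectives named in protocol section 8.2. PGE is a physician's rating and satisfaction is a separate patient survey at visit 2. Neither is derived from PF-10, yet under the SAP both denominators depend on it.

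Two kinds of valid rating can be lost:

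1. **Visit 2 attenders with no usable PF-10 at either visit.** They lose their satisfaction and PGE ratings. A PF-10 left blank at visit 1 is enough to remove a satisfaction answer given at visit 2. Because the forms are on paper, an electronic check cannot prompt the patient during completion, so incomplete forms are possible.
2. **Patients with no visit 2 PF-10.** Their visit 1 PGE is dropped although it was recorded.

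For these endpoints the reported percentages are the whole result, so the denominator is part of the finding.

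**Working it through.** **Does the departure reach every endpoint?** No. Therapeutic success and PF-10 change both need a score at each visit, so the FAS excludes the same treated patients as the protocol's rule. Only PGE and satisfaction are affected.

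**The plan's own figures (protocol section 9.5).** With p = 0.50 and n = 372, the interval is 0.50 ± 1.96 × √(0.50 × 0.50 / 372) = 44.9% to 55.1%, as stated. The total is 372 / (1 − 0.07) = 400, also as stated. Planned drop-outs are 400 − 372 = 28.

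**Visit 2 ratings.** The documents do not say how many attenders lack a usable PF-10. Three quantities are needed:

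- q, the share of 372 attenders without a usable PF-10 at one or both visits: assumed 0 to 2%.
- The satisfaction rate in the FAS: assumed 85%. The SAP plans a tabulation by category, so this stands for any grouped percentage a reader might quote.
- s, the satisfaction rate among the excluded attenders: left free between 0 and 1.

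The rate among all raters is (1 − q) × 0.85 + q × s. The FAS rate minus this is q × (0.85 − s), which lies between −0.15q and +0.85q.

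| q | Attenders lost | FAS rate minus all-rater rate |
|---|---|---|
| 0 | 0 | 0 |
| 1% | 3.7 | −0.15 to +0.85 points |
| 2% | 7.4 | −0.30 to +1.70 points |

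For scale, the 95% half-width at 85% and n = 372 is 1.96 × √(0.85 × 0.15 / 372) = 3.63 points.

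**Visit 1 PGE.** Suppose all 400 have a visit 1 rating and the 7% drop-out means no visit 2. The number dropped is then 400 − 372 × (1 − q): 28.0 at q = 0, 31.7 at 1% and 35.4 at 2%. If the planned 7% already includes unscorable PF-10 forms, the number is 28 in all.

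**How many of the 28 the treated set would recover.** The treated set needs a documented administration, and SAP section 6.7 places treatment documentation at visit 2. Some patients who never return may therefore be outside both sets. If a share d of the 28 has a documented dose, 28 × d are recovered: 0 for d = 0, 14 for d = 0.5 and 28 for d = 1. The documents do not give d.

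**Why the denominator must be named.** SAP section 7 tabulates percentages with a missing category. If all 28 drop-outs were in the treated set and missing ratings counted in the denominator, 85% of 372 would become 0.85 × 372 / 400 = 79.05%. That is a fall of 5.95 points caused by the denominator alone.

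**The case against.** The strongest reply is that the change is disclosed and prespecified, the protocol leaves analysis detail to the statistical plan, and almost nothing is lost. Satisfaction and the second PF-10 are completed at the same visit, so a patient who misses it has neither under either rule. Loss specific to the FAS needs an attender with at least half the PF-10 blank at one visit. Protocol sections 9.6, 9.7.4 and 9.8 provide for electronic checks, site queries and efforts to collect complete data. A common set also keeps the two PGE tables on largely the same patients.

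Much of this stands. The disclosure is real, and what is missing is the reason. The data checks make loss at visit 2 less likely, though they do not exclude it. It is also natural to read 372 as the number evaluable for PF-10; on that reading 28 covers the whole loss and nothing should be added. The 85% and the 0 to 2% are illustrative. The denominator shift of 5.95 points belongs to a careless correction, not to the present plan.

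It does not remove the mismatch. Comparability of the two PGE tables calls for patients with both PGE ratings, which a PF-10 condition does not select. Simplicity may be a good reason for a common set, but the SAP does not state it.

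**Conclusion.** The concern holds and is minor. The conflict between SAP section 7.4 with Table 6.3.1 and protocol section 9.7.3 is clear from the text, and no justification is given for PGE and satisfaction.

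The consequence is limited to reported percentages and denominators for two descriptive endpoints. No test, decision rule or PF-10 result changes. The visit 2 effect cannot be fixed from the documents: under the assumed 2% it stays within 1.7 points, inside the sampling uncertainty, and it may be zero. The visit 1 PGE loss is about 28 of 400 if drop-out means no second visit, or up to about 35 if unscorable forms come on top. The direction of any bias is not established.

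**What to change.** In SAP Table 6.3.1 and section 7.4:

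- Analyse satisfaction and PGE on the treated set, using the available data for each outcome.
- Base percentages on patients with an observed rating, and show the number missing as a separate count outside the denominator.
- Compare visit 1 with visit 2 PGE in patients who have both ratings. Patients rated only at visit 1 then appear in the visit 1 table alone, by design.
- Keep the FAS for the PF-10 endpoints and, if wanted, as a sensitivity set for these two.

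Record the change in section 4. If the FAS remains the main set for PGE and satisfaction, state the reason there.

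The cost is wording in sections 4, 6.3 and 7.4, one added paired PGE table, and an exception to the section 7 missing category for these two endpoints. Denominators will differ between endpoints. No new data are needed.

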9. RESEARCH METHODS

9.1 STUDY DESIGN

This is a self-controlled study design enrolling consented COPD patients who will be treated with Spiolto® Respimat® according to the approved SmPC. Patients will be enrolled consecutively and will be followed over an observational period of approx. 6 weeks. Data as listed in table 9.1:1 will be collected.

Table 9.1:1: Visit flow chart and data collection parameters.

Parameter	Visit 1; baseline visit	Visit 2; approx. 6 weeks after baseline visit
Informed Consent	X	
Inclusion / Exclusion Criteria	X	
Patient demographics (age, gender, height, and weight)	X	
Start date of COPD	X	
Number of exacerbations in the last 12 months	X	
Number of exacerbations leading to hospitalization in the last 12 months	X	
mMRC breathlessness scale, completed by the patient	X	
Past COPD therapies (6 months before visit 1)	X	
Respimat® training (yes/no)	X	
COPD severity based on GOLD assessment ¹	X	
Smoking status/history	X	X
Concomitant diseases / Comorbidities	X	X
COPD related and other relevant concomitant medication	X	X
Physical functioning (PF-10) questionnaire, completed by the patient	X	X
General condition of patient evaluated by Physician's Global Evaluation (PGE)	X	X
Safety: Adverse Drug Reactions (serious and non-serious), fatal AE, pregnancy	X	X
Patient satisfaction with Spiolto® Respimat®, completed by the patient		X
Rational for Spiolto® Respimat® treatment discontinuation (if applicable)		X
Continuation or discontinuation of treatment with Spiolto® Respimat® after the study (yes/no)		X

¹ GOLD patient group (A, B, C or D) will be automatically calculated within the eCRF based on available exacerbation history, mMRC, and GOLD spirometric classification of airflow limitation based on post-bronchodilator FEV₁ if available.

Baseline characteristics of eligible patients who gave Informed Consent, but were not treated in the study will also be collected.

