9.4 DATA SOURCES

Medical records collected through routine clinical care will be used to assess the inclusion/exclusion criteria of patients. Such medical records will be used for patient demographics, smoking history, collection of previous COPD medication, concomitant diseases, and concomitant medication.

All patients will be enrolled consecutively.

The treating physician will use the Physician’s Global Evaluation (PGE) to evaluate the general condition of the patient on an 8-point ordinal scale from 1 (very poor) to 8 (excellent). PGE will be completed before and approx. 6 weeks after treatment initiation.

The modified Medical Research Council (mMRC) scale will be used to assess the breathlessness state of the patient before the treatment. The mMRC stage (0 to 4) collected from the patient, as well as the exacerbation history and the post-bronchodilator FEV₁, will be used to automatically calculate the GOLD stage and patient group in the eCRF.

The physical functioning (PF-10) questionnaire is a subscale of the validated 36-Item Short Form Health Survey and contains 10 questions about everyday physical activity and functioning. Patients will be asked to complete the PF-10, in order to evaluate their physical functioning before and after treatment with Spiolto® Respimat®.

A patient satisfaction survey will also be completed at the end of the study, using a 7-point ordinal scale with divisions from very dissatisfied to very satisfy.

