5.2 SECONDARY ENDPOINTS

- Absolute changes in PF-10 score from visit 1 to visit 2
- General condition of the patient, evaluated by the physician (PGE score) at visit 1 and visit 2
- Patient satisfaction with Spiolto® Respimat® at visit 2

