6.6 HANDLING OF MISSING DATA AND OUTLIERS

In context of PF-10 questionnaire, missing values will be replaced with the mean of the other values, if less than half of the questions are missing for a patient. If half or more than half of the questions are missing, no score will be calculated and the PF-10 score will be marked as missing. No other missing data will be imputed.

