7. PLANNED ANALYSIS

All analyses in this study are descriptive.

For categorical variables summary tabulations of the number and percentage within each category (with a category for missing data) of the parameter will be presented. For continuous variables number of values, mean, standard deviation, minimum, median, maximum and number of missing values will be presented. Proportion rates and 95% CI will be given when appropriate.

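### PGE is rated on the same 1–8 scale at both visits, but the planned frequency tables do not show how many patients improved, stayed the same or worsened

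*SAP*

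**What the plan says.** - **Design.** Protocol 9.1: "This is a self-controlled study design enrolling consented COPD patients". There is no comparison group.
- **Measurement.** Protocol 9.4 describes an 8-point ordinal scale from 1 (worst) to 8 (best) and states: "PGE will be completed before and approx. 6 weeks after treatment initiation".
- **Endpoint.** SAP 5.2 lists "General condition of the patient, evaluated by the physician (PGE score) at visit 1 and visit 2". Protocol 8.2 and 9.1.1 are worded the same way. No PGE change endpoint is defined.
- **Analysis.** SAP 7.4: "the number and percentage of patients within each category will be displayed". Protocol 9.7.3 says that PGE at each visit, mMRC and satisfaction "are categorical variables so they will be analyzed as tabulations of frequencies". SAP 7.4 does not itself mention visits; the per-visit reading comes from SAP 5.2 and Protocol 9.7.3.
- **Analysis set.** SAP 7.4 places the secondary endpoints on the FAS, which SAP 6.3 restricts to patients with an "available PF-10 score at visit 1 and visit 2". It does not require PGE at either visit.
- **Missing data.** After the rule for PF-10 items, SAP 6.6 says "No other missing data will be imputed". SAP 7 gives every categorical table a missing category.
- **Contrast.** PF-10, also measured at both visits, has a within-patient responder rate (SAP 7.3) and a change analysis (SAP 7.4).

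Neither document plans a cross-tabulation of PGE, a PGE difference or an improved/unchanged/worsened count.

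**The concern.** A study without a control group learns from comparing each patient with himself or herself. PF-10 is analysed that way. PGE, the physician's view of the same patients over the same interval, is not, although the paired ratings are collected.

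Two per-visit tables show whether the distribution moved. They do not show whether a modest upward shift came from most patients gaining a little or from many gaining while a sizeable minority lost ground. At stake is what a named secondary outcome can tell the reader.

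A smaller matter is the denominator. The missing category shows how many FAS patients lack a rating at each visit, but not whether they are the same patients, so the number with both ratings stays unknown.

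**Working it through.** **1. The plan's own figure.** The documents give no number for PGE. The only related input is the 372 evaluable patients of Protocol 9.5, used below as the sample size. The figures there reproduce: 0.50 ± 1.96 × √(0.50 × 0.50 / 372) = 0.50 ± 0.0508, or 44.9% to 55.1%, and 372 / 0.93 = 400.

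**2. Assumed PGE distributions.** These are illustrative and not taken from the documents.

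| Category | 1 | 2 | 3 | 4 | 5 | 6 | 7 | 8 |
|---|---|---|---|---|---|---|---|---|
| Visit 1, % | 0 | 5 | 15 | 30 | 30 | 15 | 5 | 0 |
| Visit 2, % | 0 | 0 | 5 | 15 | 30 | 30 | 15 | 5 |

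Treating categories as numbers, the means are 4.5 and 5.5. The planned tables would show these two rows and nothing more.

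**3. What these rows allow.** Two cases can be checked by hand.
- Every patient moves up exactly one category: 100% improved.
- As many patients as possible stay put. The overlap of the rows is 5 + 15 + 30 + 15 + 5 = 70% (categories 3 to 7), so 70% are unchanged and 30% improved.

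The least possible share improved is the largest gap between the cumulative percentages. At categories 1–4 it is 50 − 20 = 30%, and at categories 1–5 it is 80 − 50 = 30%. For worsening, the share with visit 1 at 5 or below and visit 2 at 5 or above is at least 80 + 80 − 100 = 60%, and none of these worsened, so at most 40% did. Linear programming over all 8 × 8 tables with these margins confirms 30–100% improved, 0–70% unchanged and 0–40% worsened. These are logical limits, not likely values.

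**4. A more realistic range.** Ratings of the same patient should be positively related. A bivariate normal variable cut at the assumed percentages gives:

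| Correlation | Improved | Unchanged | Worsened |
|---|---|---|---|
| 0.2 | 62.8% | 20.9% | 16.3% |
| 0.4 | 64.8% | 22.4% | 12.9% |
| 0.6 | 67.8% | 23.7% | 8.5% |
| 0.8 | 73.7% | 23.3% | 3.0% |

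Every row produces the same planned tables. Of 372 patients, the improved count runs from 0.628 × 372 ≈ 234 to 0.737 × 372 ≈ 274, and the worsened count from 0.163 × 372 ≈ 61 to 0.0305 × 372 ≈ 11 (3.0% before rounding is 3.05%).

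**5. Would a shift table separate these cases?** Wilson 95% intervals at n = 372, treating patients as independent:
- worsened: 12.9–20.4% at correlation 0.2, against 1.7–5.3% at 0.8;
- improved: 57.8–67.6% against 68.9–77.9%.

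Neither pair of intervals overlaps, so the table would be informative at this sample size.

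**6. Dependence on the assumed margins.** With another assumed distribution, visit 1 counts 8, 30, 74, 110, 90, 44, 13, 3 (total 372) and identical totals at visit 2, the tables allow 0 to 262 improved (262 / 372 = 70.4%) and equally 0 to 262 worsened. The figures move with the margins, but in each example tried the counts are not fixed, even with complete data.

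**7. Complete pairs.** If a FAS of N patients has a ratings missing at visit 1 and b at visit 2, the number of complete pairs lies anywhere from N − a − b to N − max(a, b). The planned tables give N, a and b, but not where in that range the number falls.

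**The case against.** The strongest reply is that the plan does what it says. The objective, the outcome and the SAP endpoint all concern PGE at visit 1 and at visit 2, and tabulating each visit answers that. Where the sponsor wanted change, as for PF-10, it said so. This stands: a reader might infer that the SAP fails its own objective or endpoint, and the documents do not support that.

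A reader might also infer that the information is lost. It is not. The paired ratings will be in the database, and nothing in the SAP forbids a cross-tabulation. The limit lies in the planned tables only.

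Nor does the plan hide missing ratings: the missing category in SAP 7 lets each table account for the whole FAS. Only the count of complete pairs is absent, and since FAS patients must have PF-10 at both visits, few may lack a PGE rating.

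It is also fair to say that within-patient change is already central to the study through PF-10, and that across the realistic range the broad message (most improved, a minority worsened) would be the same. What differs is the size of that minority, roughly fivefold between the ends (16.3 / 3.0 ≈ 5.4).

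The reason given in Protocol 9.7.3, that PGE is categorical, does not rule out a paired display. A shift table is itself a frequency tabulation and involves no hypothesis test.

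**Conclusion.** The point holds as a free improvement to a descriptive secondary outcome. The planned PGE tables are consistent with the endpoint but cannot give the numbers improved, unchanged and worsened, or the number of complete pairs. The logical claim is firm. The size is not: about 63–74% improved and 16–3% worsened rests on the assumed margins, a one-category shift, correlations of 0.2 to 0.8 and 372 complete pairs. The 30–100% and 0–40% limits should not be read as plausible uncertainty.

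The primary estimate and the sample size are unaffected. It would also be wrong to infer that a shift table would show a treatment effect: regression to the mean and natural course remain, as limits of an uncontrolled design.

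**What to change.** In SAP 7.4, keep the PGE frequencies at each visit and add:

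- a descriptive visit 1 by visit 2 shift table of PGE on FAS patients with both ratings;
- the number and percentage improved (higher category at visit 2), unchanged and worsened, each with a 95% confidence interval by a named method such as Wilson. SAP 7 already allows for this: "Proportion rates and 95% CI will be given when appropriate";
- the number of complete pairs, and the number of FAS patients lacking one or both ratings.

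The full table lets readers apply another definition of improvement if they prefer one. The cost is one extra table, with no new data, no test and no change to the primary analysis. If it is added after the ratings have been examined, the report should say so.
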